9 SAMPLE SIZE JUSTIFICATION

A Bayesian adaptive design will be utilized to select the final sample size of the trial. The sample size for the study is mainly driven by the primary safety endpoint. Sample size selection interim analyses will be performed when the mITT Population reaches 80, 130, and 180 subjects. Safety outcomes at 30 days will be used as a proxy for the primary safety endpoint at each

Biosense Webster, Inc

interim for determining the sample size. The predictive probabilities for the primary safety endpoint success will be used to determine whether the sample size at the time of the interim analysis will be sufficient or if the trial will continue to the full sample of 230. The final stopping sample size of 230 was determined by fixed design power calculations for the primary safety endpoint.

Trial simulations were performed to estimate the Type-I error rate and the power for the success of the safety endpoint under a range of assumptions for the true safety rate and the assumed enrollment schedule. It is assumed that the attrition rate for the study will be negligible. For accrual rates of 1.7, 3.4, 5.1, 8.5, 11.9, 17, 20.4, 23.8, 25.5, 25.5, 25.5, 25.5, 25.5, and 25.5 patients per month for months 1 to 15 respectively, and true safety rates of 0.0% to 9.0%, the power for showing success for the primary safety endpoint is estimated to be greater than or equal to 80.0%. For a safety rate of 9.5% this power decreases to approximately 73.0%. Based on the feasibility study results referenced in the study protocol, it is unlikely that the safety event rate is higher than 9.0%. The posterior probability of the safety rate being less than or equal to 9.0% is estimated to be 0.886. Therefore, the study is expected to be sufficiently powered for the primary safety endpoint. With an assumed true effectiveness rate of 96.0% and a performance goal of 80.0%, a minimum of 80 subjects will provide higher than 99.0% power for meeting the primary effectiveness endpoint. As a result, the power estimates for the primary safety endpoint closely estimate the overall power of the study.

Since the primary effectiveness analysis is performed at a 5.0% level Type-I error and the sample size is selected independent of the effectiveness endpoint, the Type-I error for the effectiveness hypothesis is controlled at 5.0%. To estimate the Type-I error for the primary safety endpoint, we considered the hypothetical scenario that the primary safety rate is on the decision boundary (i.e. equal to 15%). Based on 25,000 trial simulations, the estimated Type-I error for this scenario was 4.7%. As the primary safety rate moves away from the decision boundary under the null hypothesis, the Type-I error for the test decreases. Since the study success is defined as meeting both primary safety and effectiveness endpoints and because the Type-I error for each of these tests is controlled at 5.0%, the overall study Type-I error will be controlled at 5.0%. (Please refer to the Appendix for more details).

Based on the simulation results, the study is adequately powered to meet the primary safety and effectiveness endpoints and that the Type-I error for the overall trial success is controlled at 5%.

10 DATA MONITORING COMMITTEE

A Data Monitoring Committee (DMC) will be constituted to monitor subject safety and provide guidance on study adaptation. The DMC charter will document roles and responsibilities of the committee and the independent statistician.

Biosense Webster, Inc

11 STATISTICAL ANALYSIS METHODS

11.1 General Conventions

Standard descriptive summaries for continuous data will include the number of observations with data, mean, standard deviation, median, 25% percentile, 75% percentile, minimum, and maximum values. For categorical data, count and percentages of observations will be provided. Summaries will be based on subjects without missing data.

11.2 Subject Disposition

Disposition and accountability of the study subjects will be summarized descriptively for the subject categories defined in section 4.4 of the protocol.

11.3 Demography and Baseline Characteristics

Subject demographics, medical history, AAD medication history and other baseline data will be summarized descriptively for all enrolled subjects as well as the safety, mITT, per protocol and NAE populations. Descriptive statistics will also be presented for roll-in subjects.

11.4 Analysis of Primary Endpoints

11.4.1 Primary Effectiveness Endpoint

The acute procedural success rate will be compared to the performance goal of 80% by using the exact test for a binomial proportion at a one-sided significance level of 5%. If the one-sided 95% lower confidence bound for the primary effectiveness rate is greater than the performance goal of 80%, the study will be considered to have demonstrated effectiveness.

The per-protocol (PP) population will be used as the analysis population for the primary effectiveness endpoint. Subjects with missing effectiveness endpoints data will be excluded in the primary analysis. The primary effectiveness endpoint will also be analyzed in the roll-in subjects.

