#### Verification of ablation procedure

- Verification of isolation of the targeted PVs by demonstrating entrance block into each targeted PV is required.

- To verify entrance block, analyze electrograms in sinus and/or atrial paced rhythm to confirm that no PV potentials are present.
- Administration of adenosine (ATP) and/or isoproterenol for each targeted PV prior to verification of entrance block is required.
- Demonstration of entrance block MUST be confirmed and documented by the Frontera Catheter. (Followed by Lasso® validation for roll-in subjects)
- The ablation procedure is considered complete when confirmation of entrance block in targeted PVs is confirmed.

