6.1.2 Primary Effectiveness Endpoints

The primary effectiveness endpoint of this study is the proportion of subjects with acute procedural success defined as confirmation of entrance block in treated pulmonary veins (PV) after adenosine and/or isoproterenol challenge (with or without the use of a focal catheter). The hypotheses to be tested for this evaluation are:

$$H_0: p_E \leq 0.80 \quad \text{vs.} \quad H_A: p_E > 0.80,$$

where p_E is the rate of acute procedural success.

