8 ANALYSIS SETS

8.1 Main Study

For the analysis of study endpoints, the analysis populations defined in the following will be used:

- **Modified Intent-To-Treat (mITT) Population:** The mITT population will consist of enrolled subjects who meet eligibility criteria and have undergone insertion of the study catheters.
- **Safety Population (SP):** The SP will consist of all enrolled subjects who have undergone insertion of the study catheters.
- **Per Protocol (PP) Population:** The PP population is a subset of the mITT population and will include subjects who comply with the following criteria:
 - are enrolled and meet all eligibility criteria
 - have undergone RF ablation with study catheters
 - are treated for the study-related arrhythmia

Neurological Assessment Evaluable (NAE) Population: The NAE Population will include at least 40 subjects who are subset of the Per Protocol Population, consent and are eligible for the required neurological assessments, and have post-ablation MRI. Assessment of incidence of new lesions requires availability of pre-and post MRI. The subjects without pre-MRI but no lesion on post-MRI will be included in the NAE population. Assessment of incidence of new deficits requires availability of pre-and post-neurological evaluation. Enrollment in the NAE population may be terminated prior to achieving the target number of subjects if study enrollment ends early after a planned interim look.

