11.4.4 Handling of Missing Data

Interim Analysis:

At the time of each interim analysis, some subjects will not have completed the full 30-day follow-up for their safety evaluation. The number of failures for the primary safety endpoint in subjects with incomplete information will be assumed to follow a beta-binomial distribution. The predicted number of failures for the primary safety endpoint will be estimated from these beta-binomial distributions for estimating the predictive probability of success for the safety endpoint.

Final Analysis:

The reasons for missingness, if available, will be listed for subjects with missing data. Patients with missing effectiveness data will be excluded from the primary effectiveness analysis.

Subjects without full follow-up required per protocol for the safety endpoint assessment will be excluded in the primary analysis unless they have experienced a PAE. Sensitivity analyses for missing data will be performed to assess the impact of missing values on the primary safety outcome and are described in the section 11.4.5.

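### The plan excludes missing effectiveness data without saying whether an RF-treated subject with no documented post-challenge entrance block is missing or a failure

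*SAP*

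**What the plan says.** SAP 6.1.2 defines the endpoint as "acute procedural success defined as confirmation of entrance block in treated pulmonary veins (PV) after adenosine and/or isoproterenol challenge", with or without a focal catheter. The protocol's section on verification of the ablation procedure requires the challenge for each targeted vein, requires the block to be documented, and adds: "The ablation procedure is considered complete when confirmation of entrance block in targeted PVs is confirmed".

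On the population, SAP 11.4.1 states: "The per-protocol (PP) population will be used as the analysis population for the primary effectiveness endpoint". Under SAP 8.1, PP subjects must be eligible, be treated for the study arrhythmia and "have undergone RF ablation with study catheters". Neither a completed procedure nor a confirmed block is required.

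On absent results, SAP 11.4.1 has "Subjects with missing effectiveness endpoints data will be excluded in the primary analysis" and SAP 11.4.4 has "Patients with missing effectiveness data will be excluded from the primary effectiveness analysis". Protocol 14.5.1 and 14.8.7 give the same rule. Both protocol sections also promise sensitivity analyses for missing effectiveness data in PP, to be described in the SAP.

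SAP 11.4.5 contains a tipping-point analysis for the safety endpoint. Its one effectiveness sensitivity analysis uses Safety Population subjects with RF delivered, on the data available. SAP 11.4.4 also lists reasons for missingness where they are known.

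**The concern.** The endpoint is scored in the laboratory at the end of the index procedure, so there is no later visit to miss. The likely reasons for an absent result are a procedure stopped after RF, an omitted challenge, a final check not done, or a result not recorded. In the first three the subject has not met the definition of success. The exclusion rule nevertheless leaves room to call the result missing and remove the subject from the denominator.

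Four kinds of record show where the gap lies:

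- Block confirmed after the challenge: success.
- Tested after the challenge and still conducting: failure, stays in.
- No RF delivered: outside PP, so the missing-data rule does not apply.
- RF delivered, no documented post-challenge result: the plan does not say.

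Only the fourth is in doubt. The safety endpoint has a guard that effectiveness lacks: under SAP 11.4.2 a subject with incomplete follow-up stays in if a primary adverse event occurred, so a known bad outcome cannot drop out. At stake are the reported success rate and the claim in protocol 14.7.2 and SAP 9 that the effectiveness test holds its 5% level.

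**Working it through.** **Inputs.** Goal 80%, exact binomial test, one-sided 5% (SAP 11.4.1). Planned true rate 96% and minimum N = 80 (protocol 14.7.2). Possible sizes 80, 130, 180 and 230 (SAP 9). I take N as the number of PP subjects. The unconfirmed share m is not in the documents; I assume 0 to 5%.

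**The plan's own figure.** The critical value c(N) is the smallest r with P(X ≥ r | N, 0.80) ≤ 0.05. At N = 80 it is 71, with actual level 2.9%. Power = P(X ≥ 71 | 80, 0.96) = 99.87%, which matches the 99.9% in protocol 14.7.2.

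**One subject can decide the result.** Suppose 80 PP subjects: 70 confirmed, 9 tested and not isolated, 1 with RF but no post-challenge check. Exact one-sided 95% lower bounds:

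- Counted as a failure: 70/80 = 87.5%, bound 79.7%, fails.
- Excluded: 70/79 = 88.6%, bound 81.0%, passes.

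**Chance of passing at the boundary.** Let exactly 80% of PP subjects be confirmed successes, a share m be unconfirmed and excluded, and the remaining 20% − m be observed failures. The rate among subjects left in is 0.80/(1 − m): 80.8% at m = 1%, 81.6% at 2%, 84.2% at 5%. With D ~ Bin(N, m) dropped,

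P(pass) = Σ_D P(D) × P(Bin(N − D, 0.80/(1 − m)) ≥ c(N − D)).

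| N | c(N) | m = 0 | 1% | 2% | 5% |
|---|---|---|---|---|---|
| 80 | 71 | 2.9% | 4.6% | 7.0% | 18.6% |
| 130 | 112 | 4.6% | 6.7% | 9.5% | 27.7% |
| 180 | 154 | 3.5% | 6.7% | 11.3% | 36.5% |
| 230 | 195 | 3.8% | 7.6% | 12.7% | 44.7% |

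At N = 80 the level is still below 5% with 1% unconfirmed; at the larger sizes it is not.

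**Near the planned rate.** N = 80 tolerates 80 − 71 = 9 failures, against 0.04 × 80 = 3.2 expected at 96%. The two rules can give different verdicts only when there are 70 or fewer confirmed successes, and P(X ≤ 70 | 80, 0.96) = 0.13%. The reported rate can still move: with 2% unconfirmed it is 0.96/0.98 = 98.0%, and if all 4% of non-successes are unconfirmed it is 0.96/0.96 = 100%, so at most 4 points too high.

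**Cost of scoring them as failures.** Power at N = 80 is P(X ≥ 71 | 80, p): 97.9% at p = 0.94, 83.6% at p = 0.95 × 0.96 = 0.912 and 81.9% at p = 0.96 − 0.05 = 0.91. At N = 230 and p = 0.91 it is 99.9%.

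**Backstop.** None of the planned analyses puts these subjects back as failures. The tipping point covers safety only. The effectiveness sensitivity analysis can bring back RF-treated subjects who were ineligible, but on available data it drops the same unconfirmed ones.

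**The case against.** The SAP nowhere says that no confirmation is coded as missing. Read strictly, the endpoint definition already makes such a subject a known non-success, so nothing is missing and the exclusion reaches only lost results. Protocol 8.2.3.1 collects, per vein, whether isolation was confirmed with the Frontera catheter, so a recorded no is possible. This stands in part. It means a reader cannot infer that the plan does drop these subjects. It does not close the gap, because the strict reading is not written down, the per-vein item is not tied to the post-challenge check, and in an unmasked single-arm study the coding could be settled after outcomes are known.

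A reader might also infer that stopped procedures in general leave the denominator, or that an absent result always reflects poor device performance. The documents support neither. A procedure stopped before RF leaves through the PP definition, and a challenge may be omitted, or a record lost, for reasons unrelated to the device. Scoring every undocumented result as a failure is therefore conservative where isolation was achieved but not recorded.

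Finally, the larger probabilities combine an assumed share with a true rate of exactly 80%, far from the planned 96%. The complication rates in protocol 1.4.1 concern other balloons and are not rates of procedures ended between RF and the challenge, so they do not supply m. This stands too.

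**Conclusion.** The plan leaves the scoring of one kind of PP subject undefined, and its exclusion rule allows that subject to be dropped. If dropped subjects are truly non-successes, the bias is upward. Its effect on the test runs from nothing at m = 0 to a pass probability of 7.0–12.7% at m = 2% and 18.6–44.7% at m = 5%, when the true confirmed rate is exactly 80%. At a true 96% the verdict would differ in about 0.1% of trials at N = 80, with the reported rate overstated by at most 4 points. These figures rest on an assumed m and on every unconfirmed subject being both excluded and a non-success.

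The stronger conclusion, that the primary test is already biased or its 5% level already lost, does not follow, because it needs a coding decision and an unconfirmed share that the documents do not state. What can be checked directly is that the effectiveness missing-data sensitivity analysis promised by the protocol for PP does not appear in the SAP.

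**What to change.** Add to SAP 11.4.1 and 11.4.4, and to protocol 14.5.1 and 14.8.7: a PP subject (RF delivered) without documented entrance block after the adenosine and/or isoproterenol challenge at the end of the index procedure counts as a failure in the primary effectiveness analysis. Keep the available-data rate as a supportive analysis, with the reasons for each absent result listed. This also meets the protocol's promise; so would a tipping-point analysis for effectiveness in PP, which is the minimum if the primary rule is left alone. The endpoint speaks of treated veins and the verification section of targeted veins; the new sentence should use one term throughout.

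The change needs wording only and no new data. The cost is a slightly lower reported rate, which is conservative where isolation was achieved but not recorded, and some power at the smallest sample size, as worked out above. Subjects tested and found not isolated, and subjects with no RF delivered, are unaffected.

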11.4.2 Primary Safety Endpoint

The PAE rate will be compared to a performance goal of 15% by using the exact test for a binomial proportion at a one-sided significance level of 5%. If the one-sided 95% upper confidence bound for the primary safety rate is less than the performance goal of 15%, the study will be considered to have demonstrated safety.

The Modified Intent-To-Treat (mITT) population will be used as the analysis population for the primary safety endpoint. Subjects without full follow-up required per protocol for the safety

endpoint assessment will be excluded in the primary analysis unless they have experienced a PAE. The primary safety endpoint will also be analyzed in the roll-in subjects.

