Sample Size	
Sample size calculations were performed using performance goals of 15% and 80% respectively for the safety and effectiveness endpoint rates. The primary safety and effectiveness endpoints will be evaluated using exact tests for binomial proportions at a one-sided 5% significance level.
 
The sample size for the study is primarily driven by the safety endpoint. An adaptive Bayesian design will be used to determine the sample size based on the safety endpoint alone. Sample size selection interim analyses will be performed after inclusion of 80, 130, 180, and 230 evaluable patients (includes all subjects who had the study catheter inserted, except roll-ins). Safety outcomes at 30 days will be used as a proxy for the primary safety endpoint at each interim analysis. The final safety analysis will be based on complete follow-up for the primary safety endpoint for all evaluable patients. Predictive probabilities of success will be used to determine whether the sample size at each interim analysis will be sufficient or if the trial enrollment will continue.
 
At the time of each interim analysis, predictive probabilities of success will be estimated using the available data from all evaluable subjects, assuming a non-informative uniform prior distribution for the primary safety rate. Enrollment will be stopped if the predictive probability of trial success at any interim is greater than 90%, or if the predictive probability of trial success with the maximum sample size is less than a futility bound of 6.5%. Otherwise, enrollment will continue until the next interim or the final sample size. Analysis of the effectiveness endpoint will be performed at the final sample size determined for the safety endpoint. Power for the effectiveness endpoint assessment is >80% at all sample sizes ≥80 subjects.
 
Operating characteristics of the adaptive design were simulated and the Type-I error for safety was shown to be less than 5%. In addition, the safety endpoint will be adequately powered for a range of safety rates. The simulation results will be provided in the Statistical Analysis Plan.

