### 4.3.2 Handling of Participant Withdrawals or Termination

If a subject is removed or withdraws from the study, the date and reason for withdrawal will be recorded on the appropriate electronic case report form (eCRF). If the subject is withdrawn due to an adverse event (AE) or serious adverse event (SAE), the Investigator should follow the subject until the AE/SAE has resolved or is considered stable.

If a subject is unable to return for an office/clinic visit or cannot be contacted by telephone, 3 separate telephone calls should be made to obtain subject related safety information. All attempts should be documented in the source documents. If the subject does not respond to the 3 telephone calls, then the investigator must send a certified letter to the subject. If the subject does not respond to the letter, then the subject will be considered “lost to follow-up” for the study.

Subjects who have signed the ICF, but are later found not to be eligible PRIOR to insertion of the study catheter can be replaced. Replacement subjects will be recruited and enrolled following the same procedures as non-replacement subjects.

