## 4.4 Subject Enrollment Disposition

- **Enrolled Subjects:** Patients who sign the informed consent form.
- **Evaluable Subjects:** All enrolled subjects who have the study catheter inserted.
- **Excluded Subjects:** Subjects who are enrolled but never undergo insertion of the study catheter. Excluded subjects will only be followed between ICF signature and exclusion for event reporting.
- **Roll-In Subjects:** Enrolled Subjects who have the study catheter inserted and RF delivered during the roll-In phase of the ablating investigator. These subjects will not be included in the main study analyses and will be analyzed separately.
- **Discontinued Subjects:** Enrolled subjects who have the study catheter inserted but do not undergo ablation (i.e., no RF energy is delivered with the study catheter). Discontinued subjects will remain in follow-up for 30 days.
- **Lost to Follow-up Subjects:** Evaluable subjects of which contact is lost after most recent visit (despite 3 documented attempts to contact the subject).
- **Withdrawn / Early Termination Subjects:** Subjects who withdraw consent for study participation or are withdrawn by the investigator, are terminated from the study prior to completion of all follow-up visits.
- **Completed Subjects:** Enrolled subjects who have not been excluded, discontinued, withdrawn, terminated early, or lost-to-follow-up from the study prior to the final study visit.

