## 11 Deviations from the Clinical Study Plan

The investigator is responsible for ensuring that the clinical investigation is conducted in accordance with the procedures and evaluations described in this protocol. The study monitors shall verify that the conduct of the study is in compliance with the currently approved protocol and applicable regulations, and shall identify any issues of non-compliance with regulations or guidelines.

Issues of non-compliance include but are not limited to repeated protocol deviations; failure to obtain proper informed consent; non-conformance to EC requirements; failure to report Adverse Events, product malfunctions and other product issues; and other non-conformance to GCP.

A protocol deviation is defined as an instance of failure to follow, intentionally or unintentionally, the requirements of the protocol (e.g. missed test or procedure, visit out of window, non-adherence to inclusion/exclusion criteria). Investigators are not allowed to deviate from the protocol. Protocol deviations will be monitored closely and will be reported per EC/CA requirement.

Under emergency circumstances, deviations from the protocol to protect the rights, safety and well-being of a subject may proceed without prior approval of the sponsor and EC. Such deviations shall be documented and reported to the sponsor and the EC as required.

All instructions described in this study protocol are to be followed. If an amendment is required, it must be made in written form and receive approval from all persons and authorities who approved the original protocol. Administrative changes (do not affect subject's benefits/risks ratio) may be inserted with abbreviated approval. All amendments will be distributed to all original protocol recipients.

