## 14 Statistical Methodology

### 14.1 Analysis Population

#### 14.1.1 Main-Study

- **Modified Intent-To-Treat (mITT) Population:** The Modified Intent-To-Treat (mITT) population consists of enrolled subjects who meet eligibility criteria and have the study catheter inserted.
- **Safety Population (SP):** The Safety Population will consist of all enrolled subjects who have undergone insertion of the study catheter.
- **Per Protocol (PP) Population:** The PP population is a subset of the mITT population and will include subjects who comply with the following criteria:

- Are enrolled and meet all eligibility criteria
  - Have undergone RF ablation with the study catheter
  - Have been treated for the study-related arrhythmia
- **Neurological Assessment Evaluable (NAE) Population:** The NAE Population will include at least 40 subjects who are subset of the Per Protocol Population, consent and are eligible for the required neurological assessments, and have post-ablation MRI. Assessment of incidence of new lesions requires availability of pre-and post MRI. Assessment of incidence of new deficits requires availability of pre-and post-neurological evaluation. Enrollment in the NAE population may be terminated prior to achieving the target number of subjects if study enrollment ends early after a planned interim look.

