### 14.2 Study Design

This clinical investigation is a prospective, multicenter, single arm clinical evaluation utilizing the Biosense Webster multi-electrode radiofrequency balloon catheter and the Biosense Webster multi-electrode circular diagnostic catheter. The sample size for the study is primarily driven by the safety endpoint. An adaptive Bayesian design will be used to determine the sample size based on the safety endpoint alone. Sample size selection interim analyses will be performed when 80, 130, 180, and 230 evaluable subjects are enrolled in the main study (mITT Population). Safety outcome at 30 days will be used as a proxy for the primary safety endpoint at each interim. The final safety analysis will be based on complete follow-up for the primary safety endpoint for all evaluable patients in the main study. Predictive probabilities of success will be used to determine whether the sample size at each interim analysis will be sufficient or if the trial enrollment will continue. Sample size simulations were performed using performance goals of 15% and 80% respectively for the safety and effectiveness endpoint rates.

At the time of each interim analysis, predictive probabilities of success will be estimated using the available data from all evaluable subjects in the mITT population, assuming a non-informative uniform prior distribution for the primary safety rate. Enrollment will be stopped if the predictive probability of trial success at any interim is greater than 90%, or if the predictive probability of trial success with the maximum sample size is less than a futility bound of 6.5%. Otherwise, enrollment will continue until the next interim or the final sample size. Analysis of the effectiveness endpoint will be performed at the final sample size determined for the safety endpoint. Power for the effectiveness endpoint assessment is >80% at all sample sizes ≥80 subjects.

The primary safety and effectiveness endpoints will be evaluated using exact tests for binomial proportions at a one-sided 5% significance level.

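### The deciding safety test runs in mITT, so a treated subject found ineligible after catheter insertion drops out with any primary adverse event, while other sections say every evaluable patient is analysed

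*SAP*

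**What the plan says.** Two sections assign a population to the primary safety test, and both name mITT. SAP 11.4.2 reads "The Modified Intent-To-Treat (mITT) population will be used as the analysis population for the primary safety endpoint", and Protocol 14.5.2 agrees. Protocol 14.1.1 says the mITT "population consists of enrolled subjects who meet eligibility criteria and have the study catheter inserted", and SAP 8.1 repeats both conditions.

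The final safety analysis is described differently elsewhere. Protocol 14.2 states: "The final safety analysis will be based on complete follow-up for the primary safety endpoint for all evaluable patients in the main study". The Sample Size row of the Protocol Summary and section 3 of the SAP Appendix say the same in nearly identical terms. Protocol 4.4 defines evaluable subjects as "All enrolled subjects who have the study catheter inserted". The Protocol Summary adds only the roll-in exclusion: the group "includes all subjects who had the study catheter inserted, except roll-ins". Neither mentions eligibility.

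Protocol 14.2 also places the interim looks "when 80, 130, 180, and 230 evaluable subjects are enrolled in the main study (mITT Population"), and later in the section again speaks of evaluable subjects as belonging to mITT.

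The Safety Population (Protocol 14.1.1, SAP 8.1) requires insertion only. SAP 11.4.5 repeats the safety analysis in it as a sensitivity analysis.

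**The concern.** A subject who has the catheter inserted and is later found ineligible is evaluable and in the Safety Population, but not in mITT. The plan allows for such subjects. Protocol 11 gives "visit out of window, non-adherence to inclusion/exclusion criteria" among its examples of deviations. The replacement rule in Protocol 4.3.2 covers only subjects who have consented "but are later found not to be eligible PRIOR to insertion of the study catheter can be replaced", so nothing in it deals with ineligibility found later.

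The trial is single-arm and unblinded, and its safety claim rests on one exact test against 15%. Eligibility can be re-examined after exposure, when the outcome is known, and an adverse event is a natural prompt for doing so. Under mITT, that review can remove the subject and the event from the deciding test.

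No other rule brings the event back into that test. The provision in SAP 11.4.2 that keeps a PAE despite incomplete follow-up works only within mITT, and the tipping-point analysis is also confined to mITT. The Safety Population repeat and the secondary safety tables (SAP 11.5.1) would show the event, but no decision depends on them.

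**Working it through.** **1. Does the test reproduce?** Inputs: performance goal 15%, one-sided 5% exact binomial test (SAP 11.4.2), N = 230 and an anticipated rate of 9.5% (SAP Appendix, section 2). The pass limit L(n) is the largest x with P(X ≤ x | n, 0.15) ≤ 0.05. L(230) = 25, with attained alpha 4.40% and exact power P(X ≤ 25 | 230, 0.095) = 79.7%. The normal approximation gives Φ[(0.055 − 1.645·√(0.15·0.85/230)) / √(0.095·0.905/230)] = 80.0%. The stated figure of at least 80% is therefore reproduced to within rounding.

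**2. What does one dropped PAE do at the limit?** The exact one-sided 95% upper bound is the 0.95 quantile of Beta(x + 1, n − x).

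| mITT result | Upper bound | With the dropped subject | Upper bound |
|---|---|---|---|
| 6/80 | 14.27% | 7/81 | 15.62% |
| 12/130 | 14.53% | 13/131 | 15.31% |
| 18/180 | 14.47% | 19/181 | 15.02% |
| 25/230 | 14.85% | 26/231 | 15.27% |

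Each result changes from pass to fail. With 5 overrun subjects the limits are 7/85, 13/135 and 19/185. Adding one subject with a PAE gives 8/86 (16.16%), 14/136 (15.62%) and 20/186 (15.24%), all failures.

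**3. How often would it matter under the stopping rules?** With x PAEs among c subjects with complete 30-day data and a uniform prior, PP(N) = P(Y ≤ L(N) − x), where Y ~ Beta-binomial(N − c, 1 + x, 1 + c − x). Enrolment stops if PP(n) > 0.90 or PP(230) < 0.065.

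The number incomplete at looks 80/130/180 is taken as those enrolled in the previous 30 days under SAP Appendix Table 1: 21/22/22 (conservative), 22/25/25 (realistic) and 28/35/37 (aggressive). A flat 25/25/25 was added. Overrun was 0, 5 or 6 subjects; the Appendix expects 5 to 6. For the realistic schedule the success cut-offs are at most 3/58, 8/105 and 14/155, and the futility cut-offs are at least 10/58, 16/105 and 21/155.

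All looks were enumerated exactly. For k excluded subjects, the Safety Population adds k to n and Bin(k, p) events, so ineligibility is unrelated to outcome. The value k = 2 is an assumption.

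| True PAE rate | mITT ends exactly at the limit | k = 2: mITT passes, Safety Population fails | k = 2: the reverse |
|---|---|---|---|
| 2.6% (feasibility) | 0.03–0.27% | 0.001–0.015% | below 0.001% |
| 5% | 0.5–2.4% | 0.05–0.25% | at most 0.006% |
| 9% | 6.3–9.2% | 1.2–1.5% | at most 0.39% |

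With k = 5, the realistic schedule, no overrun and a 5% rate, the two disagreement figures are 0.07% and 0.43%, so the direction is not fixed.

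Check against Appendix Table 2.a (realistic): power is 99.3% against 99.59% at a 5% rate, and 82.4% against 80.05% at 9%. The first-look stopping share at 5% is 67% with 22 incomplete and 48% with 25, against 45.07%. The model is approximate and the figures are illustrations.

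**4. If ineligibility is related to outcome.** Assume a fixed design with 230 inserted and an overall true rate of 15%. If a share f is ineligible with PAE rate q, the mITT rate is (0.15 − f·q)/(1 − f). For f = 2% (mITT n = 225), the mITT pass probability is 3.8%, 4.9% and 6.9% at q = 15%, 30% and 50%. For f = 5% (n = 218) it is 3.6%, 6.9% and 14.9%. The documents give neither f nor q, so this shows the mechanism only.

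**The case against.** The operative plan is not ambiguous. Both sections that assign a safety population name mITT, and Protocol 14.7 and SAP 11.4.3 count mITT for the interims, so an analyst would most likely run mITT. Within Protocol 14.2, the mITT label lets its final-analysis sentence be read consistently with 14.5.2. The SAP itself never defines evaluable. That is fair, but the reading of 14.2 works only by contradicting the definition in Protocol 4.4, and the Protocol Summary conflicts with mITT outright. The wording needs reconciling whichever set the sponsor prefers.

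The plan also limits how many subjects could be affected. Imaging, INR and pregnancy testing precede the procedure (Protocol 8.2.1), and subjects needing ablation outside the PV or CTI region are excluded before insertion (Protocol 8.2.2.3). The Safety Population repeat would put a dropped PAE beside the primary result. These points stand: the number is probably small and the event would be reported. The at-limit percentages in the table presuppose that a dropped PAE exists, so they are not flip risks in themselves.

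Finally, a narrower repair is possible: state everywhere that mITT decides and correct the use of evaluable. It would remove the contradiction. It would still allow exclusion from the deciding test after exposure.

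**Conclusion.** The concern holds. The only safety test with a success rule omits any main-study subject found ineligible after insertion. Three places describe a wider set, and Protocol 14.2 treats two differently defined sets as one. If no inserted subject is found ineligible, the sets coincide. At the feasibility rate of 2.6% (1 in 39) a change of conclusion is very unlikely. At 9%, two exclusions unrelated to outcome produce a pass in mITT and a fail in the Safety Population in about 1.2–1.5% of trials. These figures rest on assumed exclusion counts and an approximate model of the interim looks. The change should be made because it protects the denominator of an unblinded single-arm safety claim at little cost; no bias has been shown.

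**What to change.** Make the main-study Safety Population, stated explicitly as all non-roll-in subjects with the study catheter inserted, the primary set for the PAE test, the 80/130/180 interim counts and the maximum of 230. Keep the SAP 11.4.2 rule on incomplete follow-up, and keep mITT as the sensitivity analysis. The wording changes are:

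- Protocol 14.2: both places that tie evaluable subjects to mITT.
- Protocol 14.5.2 and 14.7: name the Safety Population.
- Protocol 14.8.7: already names both sets, so it only needs checking for consistency.
- SAP 9, 11.4.2 and 11.4.3: population and counts, including the 230th-subject rule.
- SAP 11.4.5: tipping point in the Safety Population; item 2 becomes the mITT repeat.
- SAP 11.4.6: safety subgroups in the Safety Population.
- Throughout: use evaluable only in the sense of Protocol 4.4 with roll-ins excluded.

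Both analyses are already planned, and the Appendix simulations do not model ineligibility, so they need not be rerun for this. The price to the sponsor is that PAEs in treated but ineligible subjects count toward the decision.
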